5.2. Study Flow Chart for patients entered from Study SGT-54-01 or SGT-54-02

Procedure	Visit 2 ^{1,2,7}	Visit 3, 4, 6, 7, 9, 10	Visit 5, 8, 11	Visit 12 (EOT ³ /EOS ⁴)	Unscheduled Visit ¹¹
Name of Visit	Baseline Day 1	Week 4, 8, 16, 20, 28, 32 ⁵ Day 29, 57, 113, 141, 197, 225	Week 12, 24, 36 ⁵ Day 85, 169, 253	Week 40 Day 281 ⁶	
Visit window		± 10 days	± 10 days	± 10 days	
Entry Criteria	X				
Sign Informed Consent	X				
Demographics	X				
Medical History/Previous Therapies	X				
Con med	X	X	X	X	X
Pregnancy Test ⁷	X	X	X	X	X
Brief Physical Examination	X		X	X	X
Cutaneous Safety Assessment and Local Tolerability Assessments	X	X	X	X	X
Administer/ Review Patient Instructions	X	X	X		X
IGA ⁸	X	X	X	X	X
Rosacea Erythema Assessment	X	X	X	X	X
Telangiectasia Assessment	X	X	X	X	X
Weigh Study Product	X	X	X	X	X
Study Product Dispensed ⁹	X	X	X		X
Provide Cleanser and Moisturizer/Sunscreen, if needed	X	X	X		X
Study Product Collected		X	X	X	
Diary Card dispensed	X	X	X		X
Diary Card collected		X	X	X	X
Adverse Events	X	X	X	X	X
Complete RosaQoL ¹⁰	X		X	X	

¹ Patient will be eligible for the extension study only after completing 12 weeks of one of the two Phase 3 studies SGT-54-01 or SGT-54-02 at the Week 12 window time (± 4 days) and missed not more than one visit of Visits 3, 4 or 5 in these studies.

² Same Visit as Visit 6 in Phase 3 Study SGT-54-01 or Study SGT-54-02. All procedures that were performed in Visit 6 of Study SGT-54-01 or Study SGT-54-02 will be captured in the Study SGT-54-07 source document.

³ EOT – end of treatment.

⁴ EOS – end of study.

⁵ All visits must be in reference to baseline and counted accordingly.

⁶ All Week 40 procedures should be completed for Patients who terminate early.

⁷ Urine test for women of childbearing potential.

⁸ For product dispensing eligibility

⁹ The dispensation and usage of the pump is based on IGA score.

¹⁰ RosaQoL is a Rosacea Quality of Life questionnaire

¹¹ Perform procedures per PI discretion.

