13.14. On-treatment (Visit 3, 4, 6, 7, 9, 10; for new patients: 12, 13) – Week 4, 8, 16, 20, 28, 32; for new patients: 36, 40, 44 - Day 29, 57, 113, 141, 197, 225; for new patients: 281, 309 (\pm 10 days)

The following procedures will be conducted at each visit:

- Observe and query the patient in a non-directive fashion about any adverse events since the previous study visit
- Query the patient about any changes in concomitant therapies since the previous study visit and update the Concomitant Therapy eCRF
- Perform the IGA described in [Section 14.1](#), rosacea erythema assessment and telangiectasia assessment described in [Sections 14.2 to 14.4](#)
- Perform Cutaneous Safety Assessment and Local Tolerability Assessment as described in [Sections 15.1 to 15.2](#)
- Perform a urine pregnancy test for all females of childbearing potential (see [Section 13.8](#))
- Review the patient's compliance with the study requirements; collect and review the Patient Diary Card
- Dispense a Diary Card to the patient
- Dispense cleanser and moisturizer with sunscreen if needed
- Record number of missed doses on the appropriate eCRF page
- Review the study product application instructions with the patient
- Collect and weigh returned study product pump
- Weigh and dispense the next pump of study product.
- Remind patient to not wear make-up to all subsequent visits
- Schedule/confirm the next study visit

13.15. Patients Who entering from Studies SGT-54-01 or SGT-54-02: End of Treatment (Visit 12) – Week 40, Day 281 (\pm 10 days) or Early Termination by the Patient or Sponsor. New Patients: End of Treatment (Visit 15) – Week 52, Day 365 (\pm 10 days) or Early Termination by the Patient or Sponsor

The following procedures will be conducted at this visit:

- Ask the patient to complete Rosacea Quality of Life (RosaQoL) questionnaire (see Appendix 2)
- Observe and query the patient in a non-directive fashion about any adverse events since the previous study visit
- Query the patient about any changes in concomitant therapies since the previous study visit and update the Concomitant Therapy eCRF
- Perform brief physical examination as described in [Section 13.7](#)
- Perform efficacy evaluations: IGA described in [Section 14.1](#), rosacea erythema assessment and telangiectasia assessment described in [Sections 14.2 to 14.4](#)
- Perform Cutaneous Safety Assessment and Local Tolerability Assessment as described in [Sections 15.1 to 15.2](#)

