8.1.2 Baseline Definition

Baseline is defined as the last non-missing assessment prior to first application in 54-01/02. For all subjects enrolled in 54-01/54-02, the baseline values from 54-01/54-02 will be considered the baseline values for calculations in 54-07. Missing results will not be flagged as baseline.

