8.1.3 Visit Windowing

For subjects receiving S5G4T-1 in 54-01/54-02, data from 54-01/54-02 will be included in summaries of 54-07. For subjects receiving vehicle in 54-01/54-02, baseline values will be sourced from 54-01/54-02 and data from follow-up visits of 54-07 will be used in summaries. The table below details the analysis visits to be summarized and the associated visits from 54-01/54-02 or 54-07 which will be sourced for each type of subject.

Analysis Visits for Efficacy and Safety Assessments

Analysis Visit	Subjects Receiving S5G4T-1 in 54-01/54-02	Subjects Receiving vehicle in 54-01/54-02
Week 4	54-01/02 - Week 4	54-07 - Week 4
Week 8	54-01/02 - Week 8	54-07 - Week 8
Week 12	54-01/02 - Week 12	54-07 - Week 12
Week 16	54-07 - Week 4	54-07 - Week 16
Week 20	54-07 - Week 8	54-07 - Week 20
Week 24	54-07 - Week 12	54-07 - Week 24
Week 28	54-07 - Week 16	54-07 - Week 28
Week 32	54-07 - Week 20	54-07 - Week 32
Week 36	54-07 - Week 24	54-07 - Week 36
Week 40	54-07 - Week 28	54-07 - Week 40
Week 44	54-07 - Week 32	Not available
Week 48	54-07 - Week 36	Not available
Week 52	54-07 - Week 40	Not available

Data from 54-07 will be mapped to the appropriate analysis visit described above based on nominal visit indications. Data from Early Termination (ET) and unscheduled visits will be determined using analysis visit windows. The analysis visit windows for ET and unscheduled visits are presented in the following table.

SGT-54-07 Analysis Visit Windows for Efficacy and Safety Assessments

Nominal Visit	Target Study Day¹	Window (Days)
Week 4	29	22 to 42
Week 8	57	43 to 70
Week 12	85	71 to 98
Week 16	113	99 to 126
Week 20	141	127 to 154
Week 24	169	155 to 182
Week 28	197	183 to 210
Week 32	225	211 to 238
Week 36	253	239 to 266
Week 40	281	267 to 294
Week 44	309	295 to 322
Week 48	337	323 to 350
Week 52	365	351 to 378

¹ Number of days since nominal Baseline visit of 54-07

Data collected at ET and unscheduled visits prior to study day 22 will not be analyzed. Data collected at ET and unscheduled visits after study day 378 will not be included in analyses.

The definition for the study day included in each study window is defined as below:

Study Day prior to Day 1 = Visit Date – Day 1 Date

Study Day on or after Day 1 = Visit Date – Day 1 Date + 1

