If an assessment’s mapped nominal visit is a visit at which the subject has data from a scheduled visit present, or if no analyses are planned for the assessment at the mapped nominal visit, the data collected at the ET or unscheduled visit will not be included in analyses.

In the event of multiple values from unscheduled or ET assessments within an analysis visit window, the value closest to the scheduled visit target study day will be used for analyses. If 2 values tie as closest to the time point (for example, one value is before and the other value is after the time point), then the later value will be selected.

Data collected at all visits will be included in the data listings with the 54-07 analysis visit presented.

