8.8.2.1 RosaQoL

The mean change in RosaQoL subscale scores from Baseline to Weeks 12, 24, 36, 48 and 52 will be summarized using descriptive statistics.

The subscores for the RosaQoL are computed as follows:

Total Score: the unweighted mean of all RosaQoL questions

Symptom subscale score: the unweighted mean of the following symptom questions

My rosacea burns or stings (item #2)

My rosacea is irritated (item #6)

My rosacea makes my skin sensitive (item #9)

My skin feels bumpy (uneven, not smooth, irregular) (item #16)

My skin flushes (item #17)

My skin gets irritated easily (cosmetics, aftershaves, cleansers) (item #18)

My eyes bother me (feels dry or gritty) (item #19)

Functional subscale score: the unweighted mean of the following functional questions

I try to cover up my rosacea (with make-up) (item #13)

I avoid certain foods or drinks because of my rosacea (item #15)

I avoid certain environments (heat, humidity, cold) because of my rosacea (item #21)

Emotion subscale score: the unweighted mean of the following emotion questions

- I worry that my rosacea may be serious (item #1)
- I worry about getting scars from my rosacea (item #3)
- I worry that my rosacea may get worse (item #4)
- I worry about side effects from rosacea medications (item #5)
- I am embarrassed by my rosacea (item #7)
- I am frustrated by my rosacea (item #8)
- I am annoyed by my rosacea (item #10)
- I am bothered by the appearance of my skin (redness, blotchiness) (item #11)
- My rosacea makes me feel self-conscious (item #12)
- I am bothered by persistence/reoccurrence of my rosacea (item #14)
- I think about my rosacea (item #20)

Each individual item should be scored as follows: 1=Never, 2=Rarely, 3=Sometimes, 4=Often, and 5=All the time. Missing data values will not be used. If a subscale has items with missing results, the subscore and the total will not be calculated.

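### SAP by-visit table shells contradict the SAP 8.1.3 map: NA sits under the wrong prior-arm column at Weeks 44–52 and at RosaQoL Week 40, and end-of-treatment vital signs have no row

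*SAP*

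**What the plan says.** **Map.** SAP 8.1.3 announces the table as follows: "The table below details the analysis visits to be summarized and the associated visits from 54-01/54-02 or 54-07 which will be sourced". Its first source column is for patients who received S5G4T-1 in 54-01/54-02 and its second is for those who received vehicle. The Week 44 row reads "Week 44 54-07 - Week 32 Not available". The Week 48 and Week 52 rows have the same pattern, sourced from 54-07 Weeks 36 and 40.

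**Shells.** Tables 14.2.1.2 (IGA), 14.2.2.2 (RosaQoL), 14.2.3 (erythema), 14.2.4 (telangiectasia) and 14.3.1.1 (tolerability) put prior vehicle first, prior E-BPO second and 54-07 overall third. Their footnote says that the visits count time from the first E-BPO dose.

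**RosaQoL visits.** SAP 8.8.2.1 says: "The mean change in RosaQoL subscale scores from Baseline to Weeks 12, 24, 36, 48 and 52 will be summarized using descriptive statistics". Table 14.2.2.2 nevertheless has a Week 40 page.

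**Early termination.** Protocol 5.2, note 6, says: "All Week 40 procedures should be completed for Patients who terminate early". Protocol 13.15 includes the questionnaire among those procedures. SAP 8.1.3 drops an early-termination or unscheduled value, among other cases, "if no analyses are planned for the assessment at the mapped nominal visit".

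**Vital signs.** Protocol 18.4.3 asks for summaries at all applicable visits, and SAP 8.9.4.3 asks for them by visit. The shell has one pooled column and pages for Weeks 12, 24, 36 and 48.

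**Baseline.** SAP 8.1.2 says: "For all subjects enrolled in 54-01/54-02, the baseline values from 54-01/54-02 will be considered the baseline values for calculations in 54-07".

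**The concern.** The map and the shells are parts of the same SAP, and they cannot both be programmed as written. A vehicle rollover first receives S5G4T-1 in 54-07 and stays at most 40 weeks, so that patient has no scheduled Week 44, 48 or 52 counted from first dose. The shells reserve those cells for exactly this group. They blank the only group that can reach 52 weeks on S5G4T-1.

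The study exists to describe safety for up to 52 weeks, and dryness, scaling, itching and burning/stinging are named safety endpoints in SAP 5 and 7.2. If the output follows the drawing, the late tolerability results appear only in the overall column. By the map that column contains only prior-S5G4T-1 patients at those visits, but nothing on the page says so.

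**Working it through.** **1. Reproduce the map.** For prior-S5G4T-1 patients, Weeks 4–12 come from the parent study, and after that analysis week = 54-07 week + 12. For prior-vehicle patients, analysis week = 54-07 week. With 54-07 visits at Weeks 4, 8, …, 40 (Protocol 5.2), this gives all 13 rows of the SAP table in both columns. Vehicle is unavailable at Weeks 44, 48 and 52; S5G4T-1 is unavailable at none.

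**2. Set the shells beside the map.** Each cell reads prior vehicle / prior E-BPO.

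| Table and week | Shell | Map and schedule |
|---|---|---|
| IGA, erythema, telangiectasia, tolerability: 44, 48, 52 | value / NA | NA / value |
| RosaQoL: 48, 52 | value / NA | NA / value |
| RosaQoL: 40 | NA / value | value / none scheduled |
| RosaQoL: 12, 24, 36 | value / value | value / value |

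The RosaQoL rows follow from the schedule. Questionnaires fall at 54-07 Weeks 12, 24, 36 and 40. Vehicle rollovers therefore have analysis Weeks 12, 24, 36 and 40. S5G4T-1 rollovers have Week 12 (parent study) and Weeks 24, 36, 48 and 52.

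**3. The prior-E-BPO cell at RosaQoL Week 40.** For these patients analysis Week 40 is 54-07 Week 28, when no questionnaire is scheduled. A patient who terminates early between Days 183 and 210 completes one, and the window table assigns it to 54-07 Week 28. The cell can therefore fill. Whether the value counts depends on whether a Week 40 analysis is planned: the shell plans one and 8.8.2.1 does not.

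**4. Vital signs.** These are taken at the physical examination (Protocol 13.7), scheduled at 54-07 Weeks 12, 24, 36 and 40. The end-of-treatment value maps to analysis Week 40 (vehicle) or Week 52 (S5G4T-1). The shell has 4 visits × 5 parameters = 20 pages, which is its stated length, so no such page exists. Missing: 2 visits × 5 parameters = 10.

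**5. Count the blocks.**
- Drawn and reversed: IGA 3 + erythema 3 + telangiectasia 3 + dryness 3 + RosaQoL total 2 = 14.
- Drawn with a wrong NA: RosaQoL total, Week 40 = 1. Together 15.
- Repeat notes, reversed: 3 further signs × 3 = 9, and 3 subscales × 2 = 6, so 14 + 9 + 6 = 29.
- Repeat notes, wrong NA: 1 + 3 subscales = 4. Together 33.

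**6. Late early-termination windows.** The window table has rows for 54-07 Weeks 44, 48 and 52 (Days 295–378), but the map uses no 54-07 visit after Week 40. The scheduled last visit is Day 281 ± 10, at latest Day 291, so only early-termination or unscheduled visits after Day 294 could fall there. The two tables do not say what happens to them.

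**7. Interval behind a change from baseline, vehicle rollovers.** Nominal interval = analysis week + 12, of which 12 weeks were on vehicle.

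| Analysis week | Interval (weeks) | Share on vehicle |
|---|---|---|
| 12 | 24 | 12/24 = 50% |
| 24 | 36 | 12/36 = 33% |
| 36 | 48 | 12/48 = 25% |
| 40 | 52 | 12/52 = 23% |

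**The case against.** Shells are mock-ups. A programmer who follows the text of 8.1.3 would probably notice the swap. The overall column is populated at every disputed visit, the listings carry all visits, and nothing in the study is tested. IGA and RosaQoL also have tables by prior arm at nominal Week 40/ET (14.2.1.1 and 14.2.2.1). Most of this stands, and it limits the weight of the point. It does not remove the contradiction, and erythema, telangiectasia and tolerability have no such second table.

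Several stronger readings are tempting, but the documents do not support them:

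- *Vehicle rollovers' last questionnaire is lost.* It stays in the overall column at Week 40 and in Table 14.2.2.1 by prior arm. Only its own cell in the by-visit table is lost.
- *The parent-study baseline is an error for vehicle rollovers.* SAP 8.1.2 states it, 8.1.3 repeats it ("For subjects receiving vehicle in 54-01/54-02, baseline values will be sourced from 54-01/54-02 and data from follow-up visits of 54-07 will be used in summaries"), and the shells footnote it. The Visit 6 questionnaire sentence in SAP 6.1 and 7.1 does not call that value the baseline for change, and 8.1.2 governs.
- *Vital signs must be split by prior arm.* All patients are assigned S5G4T-1, and SAP 8.1 promises the split only where applicable.
- *The prior arms enter 54-07 with different severity.* The protocol says only that IGA and lesion count do not limit entry. It gives no entry severity by prior arm.

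**Conclusion.** The by-visit shells are wrong as written against the SAP's own map and against their own time-axis footnote. The same reversal appears in five tables, so it is not a damaged table in the PDF. The extent is 15 drawn blocks (33 with the repeat notes) from essentially one column swap, plus two missing end-of-treatment visits for each of five vital signs and the Week 40 mismatch with 8.8.2.1.

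The consequence is a misplaced or unlabelled display, not lost data. It matters most for tolerability at Weeks 44–52, where the display by prior arm has no substitute. Adverse-event analyses are untouched. The correction should be made before the tables are programmed.

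The conclusion rests on the 8.1.3 map being the intended rule. The 40-week limit on vehicle rollovers supports that. The mixed interval behind vehicle rollovers' changes is a matter of labelling, not a fault, and the documents do not allow the size of any shift to be estimated.

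**What to change.** 1. Move NA to the vehicle column at Weeks 44, 48 and 52 in the IGA, erythema, telangiectasia and tolerability shells, and at Weeks 48 and 52 in the RosaQoL shell.
2. At RosaQoL Week 40, populate the vehicle column. Leave the prior-E-BPO cell open, with a footnote that no questionnaire is scheduled there and that only windowed early-termination or unscheduled values can appear. Add Week 40 to the visits in SAP 8.8.2.1.
3. Add vital-sign rows for Weeks 40 and 52.
4. Make the 8.1.3 map and the window table agree on values windowed to 54-07 Weeks 44–52. The sponsor should state the intended handling; this point does not call for a new exclusion rule.
5. Optional: keep the parent baseline and footnote that, for vehicle rollovers, changes from it include 12 weeks on vehicle. A labelled supplementary change from the last value before first S5G4T-1 application may be added for them.

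Items 1 to 4 cost shell edits and a few lines of SAP text, with no new data. The supplementary change in item 5 needs one more baseline flag, and its price is two baselines to keep apart.

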--	--

	
 13. Use of medicated cleansers on the face (e.g., benzoyl peroxide, salicylic acid, sulfur or triclosan) within 7 days of Baseline and throughout the study. 14. Patient consumes excessive alcohol, abuses drugs, or has a condition that could compromise the patient's ability to comply with study requirements and/or have drug or alcohol addiction requiring treatment in the past 12 months. 15. Use of topical astringents or abrasives (e.g., rubs, exfoliating cleansers and products containing salicylic acid and/or alcohol), topical preparations that contain spices or lime, medicated topical preparations (prescription and OTC products) within 7 days prior to Visit 2 (Baseline) and throughout the study. 16. Use of antipruritics (including antihistamines), spa or sauna treatments or chlorine exposure (swimming pool etc.) within 24 hours (1 day) of all study visits (Visit 2, Baseline, through End of Study). 17. Participation in any clinical study involving an investigational product, agent or device that might influence the intended effects or mask the side effects of study product, within 30 days prior to Visit 2 (Baseline) and throughout the study. 18. Previous enrollment in this study or current enrollment in this study at another participating site. 19. Employee (or employee's family member) of the research center or private practice, or patients who have a conflict of interest. 20. Patients living (e.g., siblings, spouses, relatives) in the same household cannot be enrolled in the study at the same time. 21. Use of tanning booths, sun lamps or excessive UV radiation (e.g., phototherapy, daily extended exposure or occupational exposure to the sun), sunbathing or excessive exposure to the sun 1 week (7 days) prior to Baseline and throughout the study. 22. Patients who in the opinion of the investigator, are unlikely to be able to follow the restrictions of the protocol and complete the study.
Safety Endpoints:	
 • Adverse events (AEs), including serious adverse events (SAEs) occurring at any time during the trial. • Investigator Cutaneous Safety Assessment and Local Tolerability Assessments score at any time during the trial.

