5. STUDY OBJECTIVES

The objective of this long-term safety study is to determine the nature, severity and frequency of the AE rate and the cutaneous safety and local tolerability assessments of S5G4T-1 when applied once daily, if applicable, for up to 52 weeks.

The safety endpoints to be assessed include the following:

- The frequency of both local and systemic AEs
- Investigator cutaneous safety assessment (dryness and scaling) and the local tolerability assessment (itching and burning/stinging) at Baseline and all post-baseline study visits.

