8.9.4 Other Observations Related to Safety

8.9.4.1 Cutaneous Safety Assessments

Descriptive statistics by visit will be provided for dryness and scaling.

Cutaneous Safety Assessments will be presented in a by-subject listing.

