SD	xx.xx	xx.xx	xx.xx
Median	xx.x	xx.x	xx.x
Min. to Max.	xx to xx	xx to xx	xx to xx
Total Number of Non-Instructed Missed Applications^a			
n	xx	xx	xx
Mean	xx.x	xx.x	xx.x
SD	xx.xx	xx.xx	xx.xx
Median	xx.x	xx.x	xx.x
Min. to Max.	xx to xx	xx to xx	xx to xx

^a Non-Instructed missed applications are missed doses on the CRF with reason of “Other, specify reason”.

^b Instructed missed applications are missed doses on the CRF with reason of “Per PI Instruction”.

SOURCE: USERNAME\SPONSOR\PROJECT\JOBNAME (DATE,TIME)

Table 14.3.0.1: Summary of Extent of Exposure
(Safety Population)
(Page 2 of 2)

	SGT-54-01/SGT-54-02 Vehicle Cream (N=xxx)	SGT-54-01/SG-54-02 E-BPO 5% Cream (N=xxx)	SGT-54-07 E-BPO 5% Cream (N=xxx)
Total Number of Instructed Missed Applications ^b			
n	xx	xx	xx
Mean	xx.x	xx.x	xx.x
SD	xx.xx	xx.xx	xx.xx
Median	xx.x	xx.x	xx.x
Min. to Max.	xx to xx	xx to xx	xx to xx

^a Non-Instructed missed applications are missed doses on the CRF with reason of “Other, specify reason”.

^b Instructed missed applications are missed doses on the CRF with reason of “Per PI Instruction”.

SOURCE: USERNAME\SPONSOR\PROJECT\JOBNAME (DATE,TIME)

Table 14.3.1.1: Summary of Cutaneous Safety and Tolerability Evaluations
(Safety Population)
(Page 1 of 20)

	SGT-54-01/SGT-54-02 Vehicle Cream (N=xxx)	SGT-54-01/SG-54-02 E-BPO 5% Cream (N=xxx)	SGT-54-07 E-BPO 5% Cream (N=xxx)
Dryness			
Baseline^a			
n	xx	xx	xx
0 – None	xx (xx.x%)	xx (xx.x%)	xx (xx.x%)
1 – Mild	xx (xx.x%)	xx (xx.x%)	xx (xx.x%)
2 – Moderate	xx (xx.x%)	xx (xx.x%)	xx (xx.x%)
3 – Severe	xx (xx.x%)	xx (xx.x%)	xx (xx.x%)
Week 4^b			
n	xx	xx	xx
0 – None	xx (xx.x%)	xx (xx.x%)	xx (xx.x%)
1 – Mild	xx (xx.x%)	xx (xx.x%)	xx (xx.x%)
2 – Moderate	xx (xx.x%)	xx (xx.x%)	xx (xx.x%)
3 – Severe	xx (xx.x%)	xx (xx.x%)	xx (xx.x%)
Week 8^b			
n	xx	xx	xx
0 – None	xx (xx.x%)	xx (xx.x%)	xx (xx.x%)
1 – Mild	xx (xx.x%)	xx (xx.x%)	xx (xx.x%)
2 – Moderate	xx (xx.x%)	xx (xx.x%)	xx (xx.x%)
3 – Severe	xx (xx.x%)	xx (xx.x%)	xx (xx.x%)

^a Baseline is defined as the baseline value from SGT-54-01/SGT-54-02.

^b Table summaries based analysis visits, representing time from first dose of E-BPO 5% Cream.

SOURCE: USERNAME/SPONSOR/PROJECT/JOBNAME (DATE,TIME)

Table 14.3.1.1: Summary of Cutaneous Safety and Tolerability Evaluations
(Safety Population)
(Page 2 of 20)

Dryness	SGT-54-01/SGT-54-02	SGT-54-01/SG-54-02	SGT-54-07
	Vehicle Cream (N=xxx)	E-BPO 5% Cream (N=xxx)	E-BPO 5% Cream (N=xxx)
Week 12^b			
n	xx	xx	xx
0 – None	xx (xx.x%)	xx (xx.x%)	xx (xx.x%)

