1 – Mild	xx (xx.x%)		xx (xx.x%)
2 – Moderate	xx (xx.x%)		xx (xx.x%)
3 – Severe	xx (xx.x%)		xx (xx.x%)

^a Baseline is defined as the baseline value from SGT-54-01/SGT-54-02.

^b Table summaries based analysis visits, representing time from first dose of E-BPO 5% Cream.

SOURCE: USERNAME\SPONSOR\PROJECT\JOBNAME (DATE,TIME)

Table 14.3.1.1: Summary of Cutaneous Safety and Tolerability Evaluations
(Safety Population)
(Page 5 of 20)

	SGT-54-01/SGT-54-02 Vehicle Cream (N=xxx)	SGT-54-01/SG-54-02 E-BPO 5% Cream (N=xxx)	SGT-54-07 E-BPO 5% Cream (N=xxx)
Dryness			
Week 48 ^b			
n	xx	NA	xx
0 – None	xx (xx.x%)		xx (xx.x%)
1 – Mild	xx (xx.x%)		xx (xx.x%)
2 – Moderate	xx (xx.x%)		xx (xx.x%)
3 – Severe	xx (xx.x%)		xx (xx.x%)
Week 52 ^b			
n	xx	NA	xx
0 – None	xx (xx.x%)		xx (xx.x%)
1 – Mild	xx (xx.x%)		xx (xx.x%)
2 – Moderate	xx (xx.x%)		xx (xx.x%)
3 – Severe	xx (xx.x%)		xx (xx.x%)

^a Baseline is defined as the baseline value from SGT-54-01/SGT-54-02.

^b Table summaries based analysis visits, representing time from first dose of E-BPO 5% Cream.

SOURCE: USERNAME\SPONSOR\PROJECT\JOBNAME (DATE,TIME)

Repeat these pages for [Scaling, Itching and Burning/Stinging]

Table 14.3.1.2.1: Summary of Treatment-Emergent Adverse Event Characteristics
 (Safety Population)
 (Page 1 of 2)

	E-BPO 5% Cream (N=xxx)	
Subjects Reporting Any Treatment-Emergent Adverse Event	xx	(xx.x%)
Number of Treatment-Emergent Adverse Events	xx	
Subjects Reporting Any Serious Treatment-Emergent Adverse Event	xx	(xx.x%)
Number of Serious Treatment-Emergent Adverse Events	xx	
Subjects Reporting Treatment-Emergent Adverse Event with Outcome of Fatal	xx	(xx.x%)
Number of Treatment-Emergent Adverse Events with Outcome of Fatal	xx	
Subjects Who Discontinued Study Drug Due to a Treatment-Emergent Adverse Event	xx	(xx.x%)
Number of Treatment-Emergent Adverse Events Leading to Discontinuation of Study Drug	xx	
Subjects Who Discontinued from the Study Due to a Treatment-Emergent Adverse Event	xx	(xx.x%)
Number of Treatment-Emergent Adverse Events Leading to Discontinuation of Study	xx	

Note: Treatment-emergent adverse events are those events with an onset after the first application of E-BPO 5% Cream.
 Related defined as “Definitely”, “Probably”, or “Possible”. Not Related defined as “Unlikely” or “Not related”.

SOURCE: USERNAME\SPONSOR\PROJECT\JOBNAME (DATE, TIME)

Table 14.3.1.2.1: Summary of Treatment-Emergent Adverse Event Characteristics
 (Safety Population)
 (Page 2 of 2)

	E-BPO 5% Cream (N=xxx)	

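### SAP 8.1.3 leaves some early-termination and unscheduled tolerability scores out of Table 14.3.1.1, and no worst-grade or last/ET row brings them back

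*SAP*

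**What the plan says.** SAP 8.1.3 assigns scheduled 54-07 data by nominal visit, and ET and unscheduled data by day windows counted from the 54-07 Baseline visit. Two of its rules matter here.

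- Early cut-off: "Data collected at ET and unscheduled visits prior to study day 22 will not be analyzed".
- Occupied visit: if the visit to which the value maps already has scheduled data, "the data collected at the ET or unscheduled visit will not be included in analyses".

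The values are not lost from the report altogether: "Data collected at all visits will be included in the data listings with the 54-07 analysis visit presented". For the four tolerability signs this is Listing 16.2.7.1.

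The planned summary is by visit. SAP 8.9.4.1 says "Descriptive statistics by visit will be provided for dryness and scaling", and 8.9.4.2 says the same for itching and burning/stinging. The shell, "Table 14.3.1.1: Summary of Cutaneous Safety and Tolerability Evaluations", has one Baseline row and 13 rows from Week 4 to Week 52, and a programming note repeats the dryness pages for the other three signs. It has no worst, last or ET row. IGA and RosaQoL do have a Week 40/ET display (Tables 14.2.1.1 and 14.2.2.1).

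The protocol synopsis lists as a safety endpoint "Investigator Cutaneous Safety Assessment and Local Tolerability Assessments score at any time during the trial". SAP section 5 words it as the assessments "at Baseline and all post-baseline study visits". Protocol 18.4 asks for statistics at Baseline and scheduled visits.

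**The concern.** The objective is safety and tolerability, and these four scores are a named safety endpoint. ET and unscheduled visits are where a patient with a troublesome local reaction may be seen. Protocol 5.2 (flow chart, footnote 6) asks sites to complete the Week 40 procedures, including these scores, at early termination. The SAP then keeps part of what is collected out of the only summary table.

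By-visit rows show how many patients had each grade at a given visit. They cannot show how many ever reached grade 2 or 3, nor the grade at which an early leaver left. A reader who wants either must build it from a listing.

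The early cut-off matters most for patients who had vehicle in 54-01/54-02. For them Days 1-21 of 54-07 are the first three weeks in which they can be exposed to S5G4T-1.

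**Working it through.** The plan states no figure on this point, so there is none to reproduce. I applied the 8.1.3 rules to every possible ET day.

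**Inputs**
- Windows (SAP 8.1.3): Week 4 is Days 22-42 around target Day 29 (-7/+13). Each later window is target -14 to +13, for example Week 8 at Days 43-70 around Day 57.
- Scheduled visits (SAP 6.1): Days 29, 57, ..., 281, each ±10 days.
- Assumption: every visit due before exit was attended, and ET days are spread evenly from Day 2 to the day before the Week 40 visit, excluding scheduled visit days.

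**Rule:** an ET score is omitted if day < 22, or if the scheduled visit of its window has already taken place.

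**Visits on target**
- Possible days: Days 2-280 are 279; minus 9 visit days = 270.
- Before Day 22: Days 2-21 = 20.
- Mapped visit already attended: 13 days after each of 9 visits = 9 × 13 = 117.
- Omitted: (20 + 117)/270 = 137/270 = 50.7%.

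**All visits 10 days late (Days 39, 67, ..., 291)**
- Possible days: 289 - 9 = 280.
- Omitted: 20 + 9 × 3 = 47; 47/280 = 16.8%.

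**All visits 10 days early (Days 19, 47, ..., 271)**
- Possible days: 269 - 9 = 260.
- Before Day 22: 20 - 1 (Day 19 is a visit) = 19.
- Mapped visit already attended: 21 days for Week 4 (Days 22-42) + 8 × 23 for Weeks 8-36 = 205.
- Omitted: 19 + 205 = 224; 224/260 = 86.2%.

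**Unscheduled visits.** If a patient has data at every scheduled visit, each window from Day 22 on is occupied and anything earlier is cut off. No unscheduled score can enter the table, whatever its date.

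**An uneven boundary.** A scheduled Week 4 visit on Days 19-21 is inside the ±10-day window and is tabulated under its nominal visit. An ET visit on the same day is not analysed.

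**Who can have no on-drug score at all in the table.** S5G4T-1 rollovers have their 54-01/54-02 Week 4, 8 and 12 visits sourced as on-drug data. The case therefore arises for a vehicle rollover whose only on-drug score comes from an ET or unscheduled visit on Days 2-21. That visit supplies the assessment that SAP 8.4.1 requires, and Table 14.0.2.1 would not exclude the patient for lack of a post-baseline safety assessment. The patient can thus be in the Safety Population and add nothing to the table after Baseline.

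**The case against.** The strongest reply is that the SAP does what the protocol asks. Protocol 18.4 and the synopsis analysis text want Baseline and scheduled visits, and by-visit statistics plus a full listing supply that. This stands. A reader might infer that the by-visit table breaches the protocol; it does not. The only tension is with the synopsis endpoint wording, which does not itself prescribe a worst or last summary.

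Second, reactions with consequences are summarised elsewhere. Under Protocol 15.1 and 15.2, a reaction that leads to interruption, withdrawal or a new medication is recorded as an AE, and SAP 8.9.2 tabulates AEs by severity, relationship and onset period outside these windows. This also stands. A reader might infer that tolerability-driven withdrawals vanish from the tables; they do not. What no summary captures is a score that led to no such action, and the grade on the 0-3 scale at an omitted exit visit.

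Third, many exit grades are shown. A completer's 54-07 Week 40 visit is tabulated as analysis Week 52 (S5G4T-1 rollovers) or Week 40 (vehicle rollovers). An ET score on or after Day 22 enters its row if that visit has no scheduled data. So it would be wrong to say that all ET scores are dropped.

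A reader might also infer that the windows remove unscheduled IGA values from the relapse analysis. SAP 8.8.2 counts days between IGA states and sets no restriction by visit type, so the documents do not support that reading.

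**Conclusion.** The point holds as a gap in the summaries, not as a conflict with the protocol's analysis text. Collected scores on a named safety endpoint are kept out of the table by two rules, and nothing in the table gives the worst grade per patient or the exit grade of the ETs affected.

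Its size in patients is unknown. The documents give no ET or unscheduled-visit rates; ET procedures are requested, and those at unscheduled visits are at the investigator's discretion. The shares of 51%, 17% and 86% are shares of calendar days under an even spread of ETs between visits. ETs that fall at a due visit are mostly kept (an early Week 4 visit on Days 19-21 is the exception), so the share among actual ETs could be much lower.

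A reader might infer that the omission makes the product look better tolerated. The documents do not show this: ETs include sponsor termination and reasons unrelated to the skin, and the omitted grades could be high or low. The case for change is that the summary is incomplete and cheap to complete.

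**What to change.** Keep the by-visit rows and the 8.1.3 windows. Add to Table 14.3.1.1, for each of the four signs:

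1. the worst score after the first S5G4T-1 application;
2. the last/ET score.

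Base both on all 54-07 scheduled, unscheduled and ET assessments, plus the 54-01/54-02 Week 4, 8 and 12 visits already sourced for S5G4T-1 rollovers. State in 8.1.3 or 8.9.4 that the windowing exclusions do not apply to these two rows. Show both by prior treatment group.

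Footnote three limits. The worst score rises with the number of visits (up to 13 scheduled on-drug-period visits for S5G4T-1 rollovers, 10 for vehicle rollovers). It includes periods when the patient was instructed not to dose. For itching and burning/stinging it reflects only the 24 hours before each visit (Protocol 15.2).

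The cost is two blocks per sign in one shell, a footnote and a sentence of text, with no new data collection. The drawback is the dependence on visit count. With an assumed independent chance p of grade 2 or higher per visit, P(worst ≥ 2) = 1 - (1 - p)^k. For p = 2% this is 18.3% at k = 10 and 23.1% at k = 13; for p = 5% it is 40.1% and 48.7%. That is the reason for showing the prior treatment groups separately.
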